7 PARTICIPANT ENROLLMENT

7.1 Consenting Participants

Informed consent for participation in the study must be obtained before performing any study-specific procedures.

Informed Consent Forms for enrolled participants and for participants who are not subsequently enrolled will be maintained at the study site in secure study files. Consent will be obtained by trained research study staff trained in taking informed consent. The study will be explained with the opportunity for the participant to ask questions. If a participant wishes to enter the study, a consent form will be completed and signed.

7.2 Screening for Eligibility

After informed consent has been obtained, to determine participant eligibility for enrollment in the study, screening assessments will be performed within 1 week (-21 to -14 days) prior to starting the Washout period (-14 to -1). All screening evaluations must be completed and reviewed to confirm that participants meet all eligibility criteria before Washout period and subsequent randomization on Day 0. Subjects will be asked to undergo a 2 week (-14 to -1) washout period prior to the Baseline procedure. During the screening, washout, treatment and follow-up periods, subjects will be asked to stop utilizing bleach or vinegar as a pruritus or atopic dermatitis therapy, as well as any other treatments described in the exclusion criteria and the Excluded Medications/Therapy (Appendix B).

All screening assessments are listed in the Time and Events Table (Appendix A). A participant must meet all inclusion criteria, and none of the exclusion criteria, to be enrolled and randomized in this study. The Investigator and team will maintain a screening log to record details of all persons screened and to confirm eligibility or record reasons for screening failure, as applicable.

7.3 Study Withdrawal and Withdrawal from Investigational Product and Stopping Criteria

A participant may withdraw from the study at any time at his/her own request, or may be withdrawn at any time at the discretion of the Investigator.

Reasons for withdrawal (participants who refuse to complete any remaining study visits) or discontinuation (participants who prematurely stop the application) at any time during the study may include, but are not limited, to the following:

- For safety reasons, either at the discretion of the Investigator or at the participant's request
- For protocol violations at the discretion of AOBiome
- Withdrawal of consent by the Subject
- Lost to follow-up
- Due to use of concomitant therapy that could interfere with the results of the study (the Investigator will report all such information through the CRF and decide, in accordance with AOBiome, whether the participant is to be withdrawn).

The reason for participant study withdrawal will be recorded in the electronic Case Report Form (eCRF). Data from participants withdrawing from the study will be considered evaluable up to the point at which they are withdrawn using the same criteria for evaluability as for participants who complete the study.

Study stopping rules will be implemented to stop the study for safety review in the event that:

- 1 subject reports death, or
- >2 subjects report an SAE, or
- >4 subjects experience grade 3 AEs of a similar type, or
- >6 subjects experience grade 2 AEs of a similar type

when the reported SAEs or AEs are considered possibly, probably, definitely or related to the investigational product.

Atopic Dermatitis is an active disease with known seasonal and personal histories of flares and exacerbations of the patient's underlying disease state. This includes personal histories of worsening itch and itch-scratch cycles, which can lead to localized infection and localized cellulitis. A subject's known and collected clinical history should be considered by the principal investigator when determining relationship of event to the investigational product.

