6.5.3 Weekly Average WI-NRS and AI-NRS

For WI-NRS and AI-NRS the weekly average is calculated from the daily scores. For the primary analysis the weekly average will be calculated when there is at least one recorded daily score in the corresponding week. Values from study day (as defined above) Day 1 to 7 contributes to Week 1 average, Study Day 8 to 14 to Week 2, etc. Baseline is derived as the average of the daily scores for Day -7 to -1. The average will be derived as the mean of all non-missing values during the respective time period.

Week 1 WI-NRS = (Sum of daily WI-NRS scores from Day 1 to Day 7) / (Total number of WI-NRS diaries entered from Day 1 to Day 7)

Week 2 WI-NRS = (Sum of daily WI-NRS scores from Day 8 to Day 14) / (Total number of WI-NRS diaries entered from Day 8 to Day 14)

Week 3 WI-NRS = (Sum of daily WI-NRS scores from Day 15 to Day 21) / (Total number of WI-NRS diaries entered from Day 15 to Day 21)

Week 4 WI-NRS = (Sum of daily WI-NRS scores from Day 22 to Day 28 or Day of Visit 4 - 1, whichever is earlier) / (Total number of WI-NRS diaries entered from Day 22 to Day 28 or Day of Visit 4 - 1, whichever is earlier)

Week 5 WI-NRS = (Sum of daily WI-NRS scores from Day of Visit 4 to Day of Visit 4 + 6) / (Total number of WI-NRS diaries entered from Day of Visit 4 to Day of Visit 4 + 6)

Week 6 WI-NRS = (Sum of daily WI-NRS scores from Day of Visit 4 + 7 to Day of Visit 4 + 13) / (Total number of WI-NRS diaries entered from Day of Visit 4 + 7 to Day of Visit 4 + 13)

Week 7 WI-NRS = (Sum of daily WI-NRS scores from Day of Visit 4 + 14 to Day of Visit 4 + 20) / (Total number of WI-NRS diaries entered from Day of Visit 4 + 14 to Day of Visit 4 + 20)

Week 8 WI-NRS = (Sum of daily WI-NRS scores from Day of Visit 4 + 21 to Day of Visit 4 + 27 or Day of Visit 5 - 1, whichever is earlier) / (Total number of WI-NRS diaries entered from Day of Visit 4 + 21 to Day of Visit 4 + 27 or Day of Visit 5 - 1, whichever is earlier)

The same conventions are used to calculate Week 1 to Week 8 AI-NRS.

STATISTICAL ANALYSIS PLAN

Version 3.0 12-Jan-22

Week 1 AI-NRS = (Sum of daily AI-NRS scores from Day 1 to Day 7) / (Total number of AI-NRS diaries entered from Day 1 to Day 7)

Week 2 AI-NRS = (Sum of daily AI-NRS scores from Day 8 to Day 14) / (Total number of AI-NRS diaries entered from Day 8 to Day 14)

Week 3 AI-NRS = (Sum of daily AI-NRS scores from Day 15 to Day 21) / (Total number of AI-NRS diaries entered from Day 15 to Day 21)

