7.2.4 Modified ITT Population

Modified Intent to Treat (mITT): All randomized participants who apply at least 1 dose of study medication and have at least one post-baseline evaluation on-site visit. Subjects will be grouped as randomized.

This is a change from the protocol.

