7.3.2 Clinical Trial Protocol Deviations

A summary of all major protocol deviations for mITT and Safety populations by category will be generated. Protocol deviation data will be summarized by treatment and pooled B244 treatment arm. A by-subject data listing of all protocol deviations will also be presented. Protocol deviations will be categorized as major or minor per Protocol Deviation Guidance v2.1. At the discretion of the Sponsor, major protocol deviations, as determined by a review of the data prior to unblinding of the study results and the conduct of statistical analyses, may result in the removal of a subject's data from the PP population. Biorasi and its data monitoring group as applicable will be responsible for producing the final protocol deviation and clearly identify whether or not this violation warrants exclusion from the PP population. This file will be finalized prior to hard database lock.

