The ANCOVA model for the primary endpoint change from Baseline to Week 4 in weekly average WI-NRS will have treatment group and Baseline weekly average WI-NRS as explanatory variables. Hypothesis testing will be done using a Dunnett Testing Method, applying pairwise comparisons of each respective B244 dose group to vehicle using a one-sided familywise error rate of 0.10. Treatment effect will be estimated as least squares means using vehicle as reference and adjusted for multiplicity according to the Dunnett Testing Method and presented with one-sided 90% CI.

Additionally, the two B244 dose groups will be compared by presenting the treatment difference estimated using least squares means.

Finally, in a separate analysis, the pooled B244 dose groups will be compared to vehicle using the same ANCOVA model.

STATISTICAL ANALYSIS PLAN

Version 3.0 12-Jan-22

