7.6 Handling of Dropouts or Missing Data

To account for missing daily diary entries for WI-NRS and AI-NRS, the average score for a week will be presented, where at least one score or four scores must be collected in a week for the primary and sensitivity analyses, respectively.

No other accommodations will be made for missing data other than those discussed in sections 6.5.7 and 6.5.9.

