| Investigator's Decision | n (%) | xx (xx.x) | xx (xx.x) | xx (xx.x) | xx (xx.x) | xx (xx.x) |
| Adverse Event | n (%) | xx (xx.x) | xx (xx.x) | xx (xx.x) | xx (xx.x) | xx (xx.x) |
| Pregnancy | n (%) | xx (xx.x) | xx (xx.x) | xx (xx.x) | xx (xx.x) | xx (xx.x) |
| Significant Non-Compliance | n (%) | xx (xx.x) | xx (xx.x) | xx (xx.x) | xx (xx.x) | xx (xx.x) |
| Significant Clinical Event | n (%) | xx (xx.x) | xx (xx.x) | xx (xx.x) | xx (xx.x) | xx (xx.x) |
| Incident of Unblinding | n (%) | xx (xx.x) | xx (xx.x) | xx (xx.x) | xx (xx.x) | xx (xx.x) |
| Failure to Meet Continuation Criteria | n (%) | xx (xx.x) | xx (xx.x) | xx (xx.x) | xx (xx.x) | xx (xx.x) |
| Other | n (%) | xx (xx.x) | xx (xx.x) | xx (xx.x) | xx (xx.x) | xx (xx.x) |

Table 14.1.1.1 Subject Enrollment and Disposition (All Subjects)

[1] Percentage based on the number screened.

[2] The number enrolled is equal to the sum of the number randomized and the number not assigned.

[3] Not Assigned includes subjects who passed the initial inclusion/exclusion assessment, but withdrew or were lost-to-follow-up prior to randomization.

[4] Percentage based on the number enrolled.

[5] Percentage based on the number randomized.

[6] Percentage and all subsequent percentages based on the number treated.

[7] Completed the Study indicates completion up to and including Week 8 visit.

[8] Safety Population: All subjects treated with at least 1 dose of IP.Modified Intent-to-Treat Population: All randomized participants who apply at least 1 dose of IP and have at least one post-baseline evaluation visit.

Per Protocol Population: Includes all subjects in the mITT population who administered at least 50% of IP (based on the weight of IP used calculated using the algorithm: difference in weight of all bottles dispenced and weight of all bottles returned must be at least 50% of the initial theoretical product weight i.e.(0.14 g per pump x 20 pumps per day x 28 days = 78.4 g)), have completed their Week 4 visit and did not have any major protocol deviations. Source: Listing XXXX

PROGRAM NAME: XXXXXXXXXX

DATE: HH:MM/DDMMMYYYY

Programming Note:

• Reason for Early Study Discontinuation response "Significant Clinical Event" corresponds to the CRF response "Any clinical AE, lab abnormality, or other medical condition or situation occurs such that continued participation in the study would not be in the best interest of the subject."

Table 14.1.1.2 Analysis Populations and Exclusions (All Enrolled Subjects)

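### Protocol 7.3 does not separate stopping the product from leaving the study, so a protocol violation can remove a randomised subject from the primary Week 4 test

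*Protocol*

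**What the plan says.** Protocol 7.3 distinguishes withdrawal (no further visits) from discontinuation (stopping the application), then gives a single list of reasons for both. One reason is "For protocol violations at the discretion of AOBiome". Another is concomitant therapy that could interfere with the results, where the investigator and the sponsor together settle whether the subject is withdrawn. Both reasons recur in Protocol 11.7 and SAP 4.2. Protocol 7.3 and SAP 4.2 add: "Data from participants withdrawing from the study will be considered evaluable up to the point at which they are withdrawn".

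Neighbouring sections draw the line differently. Protocol 7.4 names only loss to follow-up and withdrawn consent as causes of early termination. Protocol 8.9 treats use of an excluded therapy as a reason to stop study drug. It gives those subjects an early-termination visit and a follow-up visit, and does not say whether the daily eDiary continues.

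On the analysis side:
- SAP 7.4.2 specifies "The ANCOVA model for the primary endpoint change from Baseline to Week 4 in weekly average WI-NRS".
- SAP 6.5.3 states that "the weekly average will be calculated when there is at least one recorded daily score in the corresponding week". For Week 4 the window runs from Day 22 to Day 28, or to the day before Visit 4 if that is earlier.
- SAP 7.6 closes the subject: "No other accommodations will be made for missing data other than those discussed in sections 6.5.7 and 6.5.9".
- The definitive population (SAP 7.2.4 and 7.2.6) is mITT, whose members must "have at least one post-baseline evaluation on-site visit".
- Under SAP 7.3.2, major deviations "may result in the removal of a subject's data from the PP population". No effect on mITT is given.

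**The concern.** The primary score comes from a home diary that could keep running after a violation. If a violation ends study participation instead, the Week 4 outcome becomes missing through a decision taken after randomisation.

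That missingness need not be unrelated to itch. Appendix B of the protocol makes use of an excluded therapy a protocol violation, and several of the listed therapies are taken for itch or eczema. A subject whose itch worsens may therefore commit the very violation that permits withdrawal. The mITT analysis, described as grouping subjects as randomised, would then be partly conditioned on conduct after randomisation. SAP 7.3.2 reserves that role for the per-protocol analysis.

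**Working it through.** **1. The plan's own figure.** Protocol 12.1 asks for 160 evaluable subjects per group with a 16.7% dropout allowance. Taking 16.7% as one in six, 160 / (1 − 1/6) = 192 per group, and 3 × 192 = 576. This matches the planned total. The plan thus already allows 192 − 160 = 32 subjects per group without an evaluable outcome. It does not say how many of these may leave by sponsor or investigator decision.

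**2. What happens to a subject withdrawn for a violation.**

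| Time of withdrawal | In mITT? | Week 4 average? | In primary ANCOVA? |
|---|---|---|---|
| Before any post-baseline on-site visit | No | No | No |
| After such a visit, before Day 22 | Yes | No | No |
| After at least one diary score in the Week 4 window | Yes | Yes | Yes |

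The Early Termination Visit records an NRS (Protocol 10.6.8), but nothing in the SAP maps it to Week 4. Diary data follow the weekly windows of SAP 6.5.3 (SAP 6.5.10).

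**3. Whether another analysis recovers the second row.**
- Non-responder imputation (SAP 7.4) concerns responder endpoints. It imputes an early discontinuer only if a TEAE led to discontinuation.
- The worst-observation analysis in the SAP addendum sets the same TEAE condition, and discontinuation must precede the Week 4 visit.
- In both analyses on-treatment rescue use is a separate trigger. A subject withdrawn for a violation with neither trigger stays missing.
- The repeated-measures model (SAP 7.4.1) uses such a subject's earlier weekly averages but supplies no Week 4 value.
- The addendum's ITT analysis carries the last value forward for every randomised subject missing Week 4. It does include these subjects, as a sensitivity analysis.

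**4. Size of a possible shift.** Suppose a fraction f of one arm is withdrawn before Day 22, and those subjects' mean change (after baseline adjustment) differs by d from the mean of the whole arm. The mean of those retained then moves by f·d/(1 − f). The documents give neither f nor d, so these are assumptions:

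| f | d | Shift | Share of 0.65 |
|---|---|---|---|
| 2% | 1 | 0.02 × 1 / 0.98 = 0.020 | 3% |
| 2% | 2 | 0.02 × 2 / 0.98 = 0.041 | 6% |
| 5% | 1 | 0.05 × 1 / 0.95 = 0.053 | 8% |
| 5% | 2 | 0.05 × 2 / 0.95 = 0.105 | 16% |

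The bias in a treatment comparison is the difference between the two arms' shifts. It is zero if d = 0, or if f and d are the same in both arms.

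**5. Power.** An f of 5% is 0.05 × 192 = 9.6, about 10 subjects per arm, well inside the 32 already allowed for. No further loss should be subtracted from 160.

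**The case against.** The strongest reply is that 7.3 is ambiguous rather than wrong. The violations reason sits in a list that serves both outcomes, and 7.3 describes withdrawal as subjects refusing visits. Sections 7.4 and 8.9 suggest that a violation means, at most, stopping drug. This stands as far as it goes. But 7.3 also says a subject may be withdrawn at the investigator's discretion, and its concomitant-therapy reason has the investigator and sponsor settle whether the subject is withdrawn. Withdrawal by decision is therefore envisaged, and the ambiguity is what needs repair.

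Four stronger readings are tempting, and the documents do not support them:
- *That sponsor discretion decides who is in the test.* It is one reason among several. It matters only before the first Week 4 diary score, and violators who are not withdrawn stay in mITT.
- *That the sponsor could select by arm.* Protocol 8.4 states that sponsor staff are blinded. This limits selection by arm, though not selection on conduct or itch.
- *That power falls below plan.* The 160 per group is already net of the dropout allowance.
- *That SAP Table 14.1.1.1 proves the rule was carried through.* Its study-discontinuation rows include significant non-compliance, an unblinding incident and "Failure to Meet Continuation Criteria", and the protocol defines no continuation criteria. The table does not attribute these rows to sponsor decisions.

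It is also fair to say that the repeated-measures and last-observation analyses soften the problem, and that Protocol 11.7 asks for non-completers to be fully evaluated when possible. None of this changes the primary test.

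**Conclusion.** The concern holds in a limited form. The text permits a randomised subject to be withdrawn from the study for a violation or interfering therapy. If that happens before any Week 4 diary score, the subject drops out of the definitive test and is not imputed. Conduct after randomisation can therefore affect who is analysed.

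The size is unknown. Under the assumed 2% to 5% withdrawn from one arm, with a difference of 1 to 2 points, that arm's mean shifts by about 0.02 to 0.105. This is small to moderate against 0.65 and becomes bias only if withdrawals are selective. The case for change rests on these missing values being avoidable at little cost, not on evidence that bias occurred.

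**What to change.** In Protocol 7.3, 7.4, 8.9 and 11.7 and in SAP 4.2, separate study-drug discontinuation from study withdrawal and reconcile the passages. State that:
- a protocol violation or interfering concomitant therapy is not in itself a reason to end study participation;
- unless consent is withdrawn or the subject is lost to follow-up, such subjects continue the daily eDiary and the scheduled visits through Day 28 and follow-up;
- they are analysed as randomised, and deviations act only on per-protocol membership, as SAP 7.3.2 already provides.

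The concomitant-therapy reason must be covered as well as the violations reason, since it is the one most plainly tied to withdrawal by decision.

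Keep the study-discontinuation rows of Table 14.1.1.1 for subjects who actually leave, since relabelling them would misreport real exits. Add a tabulation by arm and reason of sponsor- or investigator-decided withdrawals before Day 22. If follow-up has already finished, this tabulation is the part that can still be done.

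No treatment, rescue or drug-stopping rule changes. The diary and visits already exist, so the cost is wording and one small table. The downside is some off-drug or non-adherent data in the primary analysis.

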7.4 Early Termination

Early termination from the study may occur due to loss to follow-up or withdrawal of consent by the subject. Participants who have discontinued the study early will be evaluated by the Investigator at the Early Termination Visit. See the list of assessments to be performed at the Early Termination Visit in the Time and Events Table (Appendix A). Participants with ongoing AEs or SAEs believed to be possibly related to investigational product (IP) will continue to be followed until resolution or for 30 days as warranted by the nature of the AE.

7.5 Lifestyle Considerations

There are no dietary or activity related restrictions for this study.

7.5.1 Use of Bland Emollients During the Study

Subjects will be allowed to use their usual choice of bland emollients (e.g., lotion, moisturizer) from screening to follow-up, on an as needed basis, using specific time of use guidelines in relation to study medication application. Subjects will be allowed to use their emollient of choice at a similar dose and frequency throughout the study if used. Any clinically significant changes in type, dose, or frequency of bland emollients will not be allowed during the study. A detailed guideline will be shared with the sites and subjects to ensure consistency in study medication treatment application and relation to body washing, emollient use, and other chemical exposure to skin.

Subjects will be encouraged not to use sunscreen on the treated lesions during participation in the study. Sunscreen should be used minimally or used sparingly while in the active treatment phase (Baseline to Week 4) of the study. Alternatively, sunscreen should be washed off prior to study medication use.

Subjects who do not have atopic dermatitis on their face may apply makeup as needed. However, those subjects who have atopic dermatitis on their face and require to use makeup will be advised to use it minimally.

8 STUDY TREATMENT

8.1 Investigational Product

Under normal conditions of handling and administration, IP is not expected to pose significant safety risks to site staff. A Material Safety Data Sheet describing the occupational hazards and recommended handling precautions will be provided to site staff if required by local laws or will otherwise be available from the Sponsor upon request.

Investigational product must be stored in a secure area under the appropriate physical conditions for the product (2-8°C). Access to and administration of the IP will be limited to the Investigator and authorized site staff. Investigational product must be dispensed or administered only to participants enrolled in the study and in accordance with this protocol (see Section 8.6).

The Investigator is responsible for study treatment accountability, reconciliation, and record maintenance. The Investigator or designated site personnel must maintain study treatment accountability records throughout the course of the study. The responsible person(s) will document the amount of study treatment received from and returned to the sponsor and the amount administered to participants. The required accountability unit for this study will be the

bottle. Discrepancies are to be reconciled or resolved.

Product name:	B244, 30ml/bottle	B244, 30ml/bottle	Vehicle, 30ml/bottle
Dosage form:	B244 suspension	B244 suspension	Vehicle solution
Unit dose strength:	1 x 10 ¹⁰ cells/ml (O.D. 5.0)	4x10 ¹⁰ cells/ml (O.D. 20.0)	50nM Na ₂ HPO ₄ - 2mM MgCl ₂ (pH 7.6)
Route/administration/duration:	Topical application BID for 28 days	Topical application BID for 28 days	Topical application BID for 28 days
Dosing instructions:	Subjects will apply a total of 10 pumps of IP per application to all affected areas twice-aday (i.e., 10 pumps in the morning and 10 pumps again at night).	Subjects will apply a total of 10 pumps of IP per application to all affected areas twice-aday (i.e., 10 pumps in the morning and 10 pumps again at night).	Subjects will apply a total of 10 pumps of IP per application to all affected areas twice-aday (i.e., 10 pumps in the morning and 10 pumps again at night).
Physical description:	Applications should occur in the morning and at night for 4 weeks. Odorless, cloudy,	Applications should occur in the morning and at night for 4 weeks. Odorless, cloudy,	Applications should occur in the morning and at night for 4 weeks. Odorless, clear, and
*	light pink suspension	light pink suspension	colorless suspension
Manufacturer/source of procurement:	AOBiome, LLC	AOBiome, LLC	AOBiome, LLC

The contents of the label will be in accordance with all applicable regulatory requirements. B244 and matching vehicle will be packaged in identical 30 ml white bottles.

